18. PHARMACODYNAMIC OUTCOMES

Pharmacodynamic analysis will be performed using the PD Analysis Set (unless specified differently underneath). Pharmacodynamic endpoints include observed, change from baseline (post baseline value – baseline value), and percent change from baseline ((change from baseline/baseline) *100%) total IgG, IgG subtypes (IgG 1, IgG 2, IgG 3 and IgG 4), and binding and blocking anti-AChR antibodies. See Section 6.3 for baseline definition.

Observed, change from baseline, and percent change from baseline values for all PD endpoints will be listed and summarized with descriptive statistics including geometric mean. Frequency table for percentage drop in IgG for ARGX-113 below cut-off per visit will be presented. Same table will be presented for subjects with QMG and MG-ADL clinical significant improvement. QMG clinical significant improvement means a drop of at least 3 points as compared to baseline and MG-ADL clinical significant improvement means a drop of at least 2 points as compared to baseline. For these mentioned frequency tables, FAS will be used.

Plots of geometric mean (\pm SD) percent change from baseline by treatment will be presented for each PD marker. Plot of evolution of percentage drop in IgG from baseline (mean +/- stdev) and delta QMG (mean +/- stdev) in function of visit will also be presented. Same plot will also be made for evolution of drop in IgG from baseline and delta MG-ADL, delta MGC and MGQoL15r in function of visit. For these evolution plots, FAS will be used. Plots will be made for ARGX-113 and for Placebo separately.

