Table 1 Schedule of Assessments

Assessments	Screening ^a	Visits																		
		Treatment period (Visit 1 to Visit 7)							Follow-Up period (Immediately after last infusion at Visit 7 to Visit 16)											
Visits	Screening Visit	V1	V2 ^{**}	V3	V4 ^{**}	V5	V6 ^{**}	V7	V8 ^{**}	V9	V10	V11	V12	V13	V14	V15	V16			
Study Day [*]		1	5±1	8±1	12±1	15±1	19±1	22±1	26±1	29±1	36±1	43±1	50±1	57±1	64±1	71±1	78±1		Safety Visit	
Informed consent ^b	X																		EoS/ED	US
Inclusion and exclusion criteria	X	X ^e																		
Medical/surgical history	X																			
Randomization		X ^e																		
Demographic Characteristics	X																			
Physical examination ^c including Height ^d and Weight	X ^{c, d}	X		X		X		X ^c		X	X	X	X			X		X ^c	X	
Vital Signs (Blood Pressure, Heart rate, Oral body temperature)	X	X ^e		X ^e		X ^e		X ^e		X	X	X	X			X		X	X	
MGQoL15 ^e	X	X	X		X		X		X	X	X	X				X		X	X	
MG-ADL ^e	X	X	X		X		X		X	X	X	X				X		X	X	
QMG ^e	X	X	X		X		X		X	X	X	X				X		X	X	
MGC ^e	X	X	X		X		X		X	X	X	X				X		X	X	
Clinical laboratory tests ^f	X	X	X		X		X		X	X	X	X				X	X	X	X	
Pharmacodynamics: anti-AChR antibodies and Immunoglobulin G and its sub-types ^g		X	X	X	X	X	X	X	X	X	X	X	X	X	X	X	X	X	X	
ECG ^h	X	X ^e							X ^e										X	X
Urinalysis	X	X ^e		X ^e		X ^e		X ^e		X	X	X	X			X		X	X	
Pharmacokinetics: Blood		X ⁱ	X ⁱ	X ⁱ	X ⁱ	X ⁱ	X ⁱ	X ⁱ	X	X	X	X	X							
Anti-drug antibodies		X ^e				X ^e		X ^e		X	X	X	X			X		X	X	
Serum Pregnancy test ^j	X																			
Urine Pregnancy test ^k		X		X		X		X				X						X	X	
Viral and bacterial tests ^l	X																			
Pharmacogenetics ^m		X		X ^m																
Administration of ARGX-113 or placebo ⁿ		X		X		X		X												
Suicidality assessment ^o	X	X	X		X		X		X	X	X	X	X	X	X	X	X	X	X	
Concomitant therapies ^p	X	X	X	X	X	X	X	X	X	X	X	X	X	X	X	X	X	X	X	
Adverse events ^p	X	X	X	X	X	X	X	X	X	X	X	X	X	X	X	X	X	X	X	

argenx

ARGX-113-1602, Version 2.0

ARGX-113

Abbreviations: BMI = Body Mass Index; ECG = Electrocardiogram; ED = Early Discontinuation; EoS = End-of-Study; EoT = End-of-Treatment; FU = Follow-Up; MG-ADL = Myasthenia Gravis-Activities of Daily Living; QMG = Quantitative Myasthenia Gravis score; MGC = Myasthenia Gravis Composite score; MGQoL15r = 15-item quality of life scale for Myasthenia Gravis [Revised version]; US = Unscheduled; V = Visit.

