In preclinical studies, ARGX-113 demonstrated high potency and rapid onset of action in IgG autoantibody reduction. In murine *in vivo* disease models, ARGX-113 demonstrated a high therapeutic potential linked to a rapid clearance of IgG autoantibodies. Studies in cynomolgus monkeys confirmed this rapid onset of IgG reduction, and demonstrated specificity of this effect as IgA, IgM, and albumin levels were not affected.

In addition, following administration of a single dose of 10 mg/kg in healthy volunteers there was a 55% decrease of serum IgG levels. Six doses of 10 mg/kg administered every four days were considered safe, well tolerated and resulted in a maximum effect on serum IgG decrease.

[figure not shown]
[figure not shown]
[figure not shown]
Myasthenia gravis is considered to be a highly autoantibody driven disease. ARGX-113 is postulated to be a highly specific targeted therapy to reduce the autoantibody levels. Results from the Phase I study indicate it is safe and tolerable based on data from healthy volunteers. Therefore, ARGX-113 is believed to be a promising treatment to reduce autoantibodies in MG patients.

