10.4.2.3 Analysis of Pharmacodynamic Parameters

Continuous PD parameters summarized with descriptive statistics including geometric mean. Pharmacodynamic parameters include total IgG, IgG subtypes, anti AChR antibodies. Further details will be described in the SAP.

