17.1. PHARMACOKINETIC CONCENTRATIONS

A listing of PK blood sample collection times as well as derived sampling time deviations will be provided.

A subject listing of all concentration-time data will be presented. Individual subject concentration-time data will be graphically presented on linear and semi-logarithmic scales.

Document:

CCI

Author:

PPD

Version Number:

1.0

Version Date:

06 Oct 2017

Template No: CCI

Effective Date: 01Apr2016

Reference: CCI

Copyright © 2009, 2010, 2012, 2016 Quintiles Transnational Corp. All rights reserved.

The contents of this document are confidential and proprietary to Quintiles Transnational Corp. Unauthorized use, disclosure or reproduction is strictly prohibited.

Plasma concentrations of ARGX-113 will be summarized by nominal time point using the following statistics:

- Number of observations (n)
- Number of observations \geq lower limit of quantification (LLOQ)
- Arithmetic mean
- SD
- Geometric mean
- Geometric SD
- Minimum
- Median
- Maximum

If warranted by the data, concentrations may be further summarized by ADA presence. Concentrations of ARGX-113 that are below the limit of quantification (BLQ) will be set to the lower limit of quantification (LLOQ) for the computation of descriptive statistics. A figure of geometric mean concentration-time (in days) data (\pm SD, as appropriate; from the start of the first infusion) will be presented on linear and semi-logarithmic scales.

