19. ADDITIONAL ASSESSMENT OF IMMUNOGLOBULINS

The observed, change from baseline, and percent change from baseline of IgA, IgM, IgE and IgD will be listed and summarized with descriptive statistics, using PD Analysis Set.

See Section 6.3 for baseline definition.

Document:	CCI	Version Number:	1.0
Author:	PPD	Version Date:	06 Oct 2017
Template No:	CCI	Reference:	CCI
Effective Date:	01Apr2016		

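### SAP Section 18 orders a geometric mean of change and percent change from baseline for every PD marker, but any fall makes those values negative and the statistic undefined

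*SAP*

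**What the plan says.** Protocol 10.4.2.3 is brief: "Continuous PD parameters summarized with descriptive statistics including geometric mean". It names total IgG, the IgG subtypes and anti-AChR antibodies, and leaves further detail to the SAP.

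SAP Section 18 supplies that detail. It defines change as the post-baseline value minus the baseline value, and then "percent change from baseline ((change from baseline/baseline) *100%) total IgG", the IgG subtypes, and the binding and blocking anti-AChR antibodies. For tables, it lists observed values, change, and "percent change from baseline values for all PD endpoints will be listed and summarized with descriptive statistics including geometric mean". For figures, geometric mean (± SD) "percent change from baseline by treatment will be presented for each PD marker".

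SAP Section 19 treats IgA, IgM, IgE and IgD differently. The observed values, change and "percent change from baseline of IgA, IgM, IgE and IgD will be listed and summarized with descriptive statistics", with no geometric mean named.

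**The concern.** A geometric mean is computed on logarithms, so every value must be strictly positive. Under the SAP's sign convention a patient whose marker falls contributes a negative number and a patient with no change contributes zero. The treatment is meant to produce falls. Protocol 2.3 reports that "following administration of a single dose of 10 mg/kg in healthy volunteers there was a 55% decrease of serum IgG levels". In the active arm the statistic should therefore fail at most on-treatment visits. In the placebo arm values should scatter around zero, and it should fail there too.

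If IgG in the Section 18 evolution plots is read as total IgG, the geometric-mean percent-change plot is the only marker-specific figure that Section 18 names for six of the seven markers: IgG 1 to 4 and the two anti-AChR antibodies. Whoever programs it would have to choose a substitute after the SAP is final, and the possible substitutes give different answers.

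**Working it through.** The plan states no figure to reproduce here. The check applies the definition of the statistic to the SAP's own formulas.

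**Inputs**

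- Change = post − baseline; percent change = 100 × change / baseline (SAP Section 18; SAP 6.7 uses the same sign).
- Seven markers: total IgG, IgG 1 to 4, binding and blocking anti-AChR antibodies (SAP Section 18).
- PD sampling at every visit from Visit 1 to Visit 16 (Protocol Table 1, row "Pharmacodynamics: anti-AChR antibodies and Immunoglobulin G and its sub-types"). This gives 15 post-baseline visits, or 11 without optional Visits 2, 4, 6 and 8.
- 12 subjects planned per arm (SAP 7.2). Ten per arm is also shown, from Protocol Appendix 14.6.

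**Definition.** Geometric mean = exp(mean(log x)), which needs every x > 0. Percent change is positive only if post > baseline. A cell is therefore defined only if every patient in that arm rose above baseline at that visit.

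**Number of outputs affected.** 7 markers × 2 quantities × 15 visits × 2 arms = 420 cells, or 7 × 2 × 11 × 2 = 308 at the non-optional visits, plus seven marker plots. With a positive baseline, change and percent change always share a sign. The 420 cells are thus 7 × 15 × 2 = 210 marker-visit-arm combinations, each counted twice.

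**Chance that a cell is defined.** If each patient independently has probability p of a rise, the chance is pⁿ. The values of p are assumed, because the documents give none.

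| p (rise) | n = 12 | n = 10 |
|---|---|---|
| 0.5 | 0.00024 | 0.00098 |
| 0.7 | 0.0138 | 0.0282 |
| 0.9 | 0.282 | 0.349 |

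The first row is the natural case for placebo with no drift. An active arm in which IgG falls sits well below it.

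**Small example.** Take illustrative percent changes of −60, −55, −50 and −45.

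- As specified: the logarithm of each value is undefined, so there is no result.
- Using the root of the product instead: 60 × 55 × 50 × 45 = 7,425,000, and the fourth root is 52.2. An even number of negatives gives a positive product, so this would show a rise of about 52%.
- On the ratio scale: ratios 0.40, 0.45, 0.50 and 0.55; exp(mean(log ratio)) = 0.4717; 100 × (0.4717 − 1) = −52.8%.
- Arithmetic mean: −52.5%.

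**What dropping non-positive values would do.** In single simulated arms of 12, with an assumed log-SD of the post/baseline ratio of 0.1 to 0.3 on active and 0.1 to 0.2 on placebo:

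- Active, true fall 55%: all 12 values were negative at each spread, so nothing remains.
- Placebo, no true change: 5 of 12 values were zero or below at each spread. The geometric mean of the risers alone was +6.3% (log-SD 0.1) and +4.8% (log-SD 0.2). The arithmetic means of all 12 were +1.6% and +3.1%.

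**The case against.** The strongest reply is that geometric mean percent change is an accepted label for 100 × (geometric mean ratio − 1), and that the plot sentence is shorthand for it. On that view a formula is missing and nothing is wrong. The author may well have meant this, but Section 18 gives a different formula for percent change and mentions no ratio, logarithm or back-transformation. Where the SAP does work on the log scale, as for the geometric coefficient of variation in 17.2, it writes the formula out. Plotting the fall as a positive number does not help either, because the failure moves to the patients who rise.

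Several points stand in part:

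- The case is certain for percent change, because the plot sentence attaches the geometric mean to it directly. For raw change it rests on the natural reading of the table sentence.
- The mock shells referred to in SAP Section 8 are not among the documents and might handle these rows. That cannot be assumed.
- The cell count is an upper bound, and the probabilities of a rise are assumed. The sign argument needs neither.
- The protocol allows other graphs as appropriate, and SAP Section 1 requires deviations to be described and justified in the report. A substitute would be disclosed, though not pre-specified.
- No test, sample size or decision rule depends on these outputs.

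**Conclusion.** The concern holds. As Section 18 is written, the geometric mean of percent change, and on the natural reading of change, does not exist for any arm and visit at which even one patient falls or stays level. That will be nearly every cell in both arms. The conclusion follows from the SAP's definitions and the arithmetic of logarithms. The assumed probabilities and simulated spreads only illustrate it.

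The consequence is limited. PD is a secondary, descriptive objective. The arithmetic mean, SD, median and range, the geometric mean of observed levels, the IgG evolution plots (mean ± SD), the IgG frequency table and the listings all remain valid. What is lost is a pre-specified geometric-mean summary and figure of relative change for each marker. This should be corrected before database lock, but it does not threaten the study's conclusions.

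**What to change.** Amend SAP Section 18 and the matching shells as follows:

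- Use the geometric mean for observed values and for the post/baseline ratio only, computed as exp(mean(log(post/baseline))).
- Report 100 × (ratio − 1) as the geometric mean percent change and plot that quantity. Label the bars as either back-transformed 95% confidence limits or geometric SD limits. A plain ± SD does not match a geometric mean.
- Summarise raw change and raw percent change with arithmetic mean, SD, median and range.
- State how a zero or below-quantification antibody result enters the log ratio. The rule in SAP 17.1 covers ARGX-113 concentrations only.

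The cost is a few sentences in the SAP and a shell edit before database lock. No new data or assessments are needed.

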19. ADDITIONAL ASSESSMENT OF IMMUNOGLOBULINS

The observed, change from baseline, and percent change from baseline of IgA, IgM, IgE and IgD will be listed and summarized with descriptive statistics, using PD Analysis Set.

See Section 6.3 for baseline definition.

Document:	CCI	Version Number:	1.0
Author:	PPD	Version Date:	06 Oct 2017
Template No:	CCI	Reference:	CCI
Effective Date:	01Apr2016		

20. ANTI-DRUG ANTIBODIES (ADA) ANALYSES

ADA will be summarized by frequency and percentages of response, using PD Analysis Set. The following statistics will be presented for ADA response for each treatment

- Proportion
- 95% Confidence Interval of Proportion (using Clopper-Pearson exact method)
- Difference in proportions (ARGX-113 – Placebo)
- 95% CI of Difference
- p-value (using Fisher's Exact Test)

21. PHARMACOGENETIC OUTCOMES

For subjects who signed a separate Pharmacogenetic ICF, FcRn polymorphisms will be examined as a part of exploratory assessments. Assessment of FcRn polymorphism will be done to examine the gene sequence, gene expression, transcription and polymorphism. No genetic testing or genetic profiling will be done.

Descriptive statistics will be used to study the genetic makeup of these subjects. Any categorical variables (if available) will be summarized by frequency (percentage) under each category. A listing of all Pharmacogenetic outcomes will be presented.

Document: CCI
Author: PPD
Version Number: 1.0
Version Date: 06 Oct 2017
Template No: CCI
Effective Date: 01Apr2016
Reference: CCI

APPENDIX 1. PARTIAL DATE CONVENTIONS

Imputed dates will NOT be presented in the listings.

Algorithm for Treatment Emergence of Adverse Events:

START DATE	STOP DATE	ACTION
Known	Known	If start date and time < study med start date and time, then not TEAE If start date and time >= study med start date and time, then TEAE
	Partial	If start date and time < study med start date and time, then not TEAE If start date and time >= study med start date and time, then TEAE
	Missing	If start date and time < study med start date and time, then not TEAE If start date and time >= study med start date and time, then TEAE
Partial, but known components show that it cannot be on or after study med start date and time	Known	Not TEAE
	Partial	Not TEAE
	Missing	Not TEAE
Partial, could be on or after study med start date and time	Known	If stop date and time < study med start date and time, then not TEAE If stop date and time >= study med start date and time, then TEAE
	Partial	Impute stop date and time as latest possible date and time (i.e. last day of month if day unknown or 31st December if day and month are unknown), then: If stop date and time < study med start date and time,

Document:

CCI

Author:

PPD

Version Number:

1.0

Version Date:

06 Oct 2017

Template No: CCI

Reference: CCI

Effective Date: 01Apr2016

Copyright © 2009, 2010, 2012, 2016 Quintiles Transnational Corp. All rights reserved.

The contents of this document are confidential and proprietary to Quintiles Transnational Corp. Unauthorized use, disclosure or reproduction is strictly prohibited.

START DATE	STOP DATE	ACTION
		then not TEAE If stop date and time >= study med start date and time, then TEAE
	Missing	Assumed TEAE
Missing	Known	If stop date and time < study med start date and time, then not TEAE If stop date and time >= study med start date and time, then TEAE
	Partial	Impute stop date and time as latest possible date and time (i.e. last day of month if day unknown or 31st December if day and month are unknown), then: If stop date and time < study med start date and time, then not TEAE If stop date and time >= study med start date and time, then TEAE
	Missing	Assumed TEAE

Document:
Author:

CCI
PPD

Version Number:
Version Date:

1.0
06 Oct 2017

Template No:
Effective Date: 01Apr2016

Reference: CCI

Algorithm for Prior / Concomitant Medications:

START DATE	STOP DATE	ACTION
Known	Known	If stop date < study med start date, assign as prior If stop date >= study med start date, assign as concomitant
	Partial	Impute stop date as latest possible date (i.e. last day of month if day unknown or 31 st December if day and month are unknown), then: If stop date < study med start date, assign as prior If stop date >= study med start date, assign as concomitant
	Missing	If stop date is missing could never be assumed a prior medication hence assign as concomitant.
Partial	Known	Impute start date as earliest possible date (i.e. first day of month if day unknown or 1 st January if day and month are unknown), then: If stop date < study med start date, assign as prior If stop date >= study med start date, assign as concomitant
	Partial	Impute start date as earliest possible date (i.e. first day of month if day unknown or 1 st January if day and month are unknown) and impute stop date as latest possible date (i.e. last day of month if day unknown or 31 st December if day and month are unknown), then: If stop date < study med start date, assign as prior If stop date >= study med start date, assign as concomitant
	Missing	Impute start date as earliest possible date (i.e. first day of month if day unknown or 1 st January if day and month are unknown), then: If stop date is missing could never be assumed a prior medication hence assign as concomitant.
Missing	Known	If stop date < study med start date, assign as prior If stop date >= study med start date, assign as concomitant
	Partial	Impute stop date as latest possible date (i.e. last day of month if day unknown or 31 st December if day and month are unknown), then: If stop date < study med start date, assign as prior If stop date >= study med start date, assign as concomitant
	Missing	Assign as concomitant

Document:
Author:

CCI
PPD

Version Number:
Version Date:

1.0
06 Oct 2017

Template No:
Effective Date: 01Apr2016

CCI
